2.2.3. Exploratory Objective

- To evaluate effects of cryoablation plus nirogacestat on quality of life.
- To correlate changes during treatment with response using the Nanostring CosMX SMI on biopsy samples.

2.3. ClinicalTrials.gov Registration, Outcomes, and Results

This study has been registered on ClinicalTrials.gov, and results will be reported. The US Food and Drug Administration (FDA) has approved nirogacestat (Ogsiveo™) for the treatment of desmoid tumor. The principal investigator of this study has submitted IND 164301 to the FDA. The Visual-ICE Cryoablation System, which will be used to perform cryoablation for this study, has FDA 510(k) clearance. Cryoablation is recognized by National Comprehensive Cancer Network (NCCN) as a viable procedure for desmoid tumor.

2.3.1. Data Sharing Statement

Pursuant to the International Committee of Medical Journal Editors (ICMJE), the following statement, regarding sharing of individual subject data (ie, participant-level data) generated by interventional clinical trials, is provided.

It is not planned that individual participant data, including data dictionaries, will be made publicly available. Individual participant study data judged by the investigator to be pertinent to a participant's understanding of their medical condition and treatment options will be shared with that participant. Otherwise and as such, details of what, or when, or by what mechanism, data and/or documents will be shared, who would share such data, or for what purposes or analyses, are not available or not applicable.

Although not individual participant data, pursuant to the requirements of [42CFR§11.48\(a\)\(5\)](#) (if applicable), the final IRB-approved protocol document with statistical analysis will be made available in the ClinicalTrials.gov results record.

2.3.2. Outcome Measures for ClinicalTrials.gov Results Reporting

2.3.2.1. Primary Outcome

- **Primary Outcome Measure Title:** Clinical Benefit per RECIST v1.1

Description: Clinical benefit (CB) is defined as the number of participants assessed with a complete response (CR), partial response (PR), or stable disease (SD) within 1 year and with no evidence of loss of response nor progression within that year.

Response & progression will be assessed according to the Revised Response Evaluation Criteria in Solid Tumors (RECIST)v1.1, as follows:

RECIST v1.1:

- CR=Disappearance of all lesions
- PR= $\geq 30\%$ decrease in diameter of target lesions
- Progressive disease (PD)=20% increase in diameter of target lesion; progression of non-target lesion; or ≥ 1 new lesion(s)

For the overall outcome:

- SD=Changes not meeting above criteria
- Overall Response (OR)=CR+PR
- CB=CR+PR+SD

The outcome is a number without dispersion.

- **Time Frame:** 1 year
- **Completion of Primary Outcome:** Based on the projected accrual of 20 subjects within 24 months, the last datum for the primary objective / outcome is expected to be obtained approximately 44 months from the time the study opens to accrual.

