Nirogacestat had a manageable safety profile and was tolerated by the majority of patients. The frequency of patients that experienced at least 1 TEAE was similar between treatment arms (69 patients [100%] in the nirogacestat arm and 69 patients [96%] in the placebo arm). In the nirogacestat arm, the majority (95%) of TEAEs were Grade 1 or Grade 2. The most frequently reported (> 30% of patients) TEAEs in the nirogacestat arm were diarrhea, nausea, fatigue, hypophosphatemia, and rash maculo-papular. Events of ovarian dysfunction (as defined by the preferred terms of menopause, premature menopause, ovarian failure, and amenorrhea) were also commonly reported in women of childbearing potential (27/36 [75%]) receiving nirogacestat. More Grade \geq 3 events occurred in the nirogacestat arm compared to placebo; diarrhea had the greatest imbalance in incidence with 16% in the nirogacestat arm vs 1% in placebo. A total of 21 patients (15%) experienced an SAE, including 14 patients (20%) in the nirogacestat arm and 7 patients (10%) in the placebo arm. The only preferred term (PT) reported as serious by > 1 patient in the nirogacestat arm was premature menopause (3 patients). One death occurred; this event of sepsis was in the placebo arm and was considered by the investigator to be unrelated to study treatment. Sixteen (23%) patients receiving nirogacestat had TEAEs leading to study treatment discontinuation; 2 of these 16 patients also had clinical progression as the primary reason for treatment discontinuation and the reported TEAEs were manifestations of the progression. Excluding the discontinuations due to clinical progression, 14 (20%) patients discontinued due to TEAEs. The TEAEs leading to discontinuation of study treatment of > 1 patient in the nirogacestat arm were diarrhea, premature menopause, ALT increased, and AST increased. The overall benefit / risk balance for nirogacestat treatment of adult patients with DTs was favorable, with a substantial reduction in the risk of disease progression, an increase in the objective response rate, and significant and clinically meaningful improvements in pain, DT-specific symptom burden and their impact on patient lives, physical functioning, role functioning, and health-related quality of life, balanced with a manageable safety profile.

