2.3.2.2. Secondary Outcomes

- **Outcome 2 (Secondary) Title:** Clinical Benefit per mRECIST

Description: Clinical benefit (CB) is defined as the number of participants assessed with a complete response (CR), partial response (PR), or stable disease (SD) within 1 year and with no evidence of loss of response nor progression within that year.

Response & progression will be assessed according to the modified Revised Response Evaluation Criteria in Solid Tumors (mRECIST), as follows.

mRECIST:

- CR=Disappearance of intratumoral enhancement
- PR= $\geq 30\%$ decrease in the diameter of target lesion(s)
- PD=An increase of $>20\%$ in the diameter of target lesion.

The outcome is the number of participants alive after 1 year and without PD per mRECIST, a number without dispersion.

Time Frame: 1 year

- **Outcome 3 (Secondary) Title:** Progression-free Survival (PFS)

Description: Progressive-free survival (PFS) is an assessment of the number of participants at a specific time who remain alive and without tumor progression.

Progressive disease (PD) will be assessed according to Revised Response Evaluation Criteria in Solid Tumors (RECIST)v1.1, or, for tumors assessed with MRI enhancement, modified RECIST (mRECIST) defined as follows:

RECIST v1.1:

- PD=20% increase in diameter of target lesion; progression of non-target lesion; or ≥ 1 new lesion(s)

mRECIST:

- PD=An increase of $>20\%$ in the diameter of target lesion.

The outcome is the number of participants alive after 1 year and without PD per RECIST or mRECIST, a number without dispersion.

Time Frame: 1 year

- **Outcome 4 (Secondary) Title:** Objective Response

Description: Objective response (OR) is defined as the number of participants assessed with a complete response (CR) or partial response (PR) within 1 year and with no evidence of loss of response nor progression within that year. Response & progression will be assessed according to the Revised Response Evaluation Criteria in Solid Tumors (RECIST)v1.1, or, for assessed with MRI enhancement, modified RECIST (mRECIST) as follows:

RECIST v1.1:

- CR=Disappearance of all lesions
- PR= $\geq 30\%$ decrease in diameter of target lesions
- Progressive disease (PD)=20% increase in diameter of target lesion; progression of non-target lesion; or ≥ 1 new lesion(s)

mRECIST:

- CR=Disappearance of intratumoral enhancement
- PR= $\geq 30\%$ decrease in the diameter of target lesion(s)
- PD=An increase of $>20\%$ in the diameter of target lesion.

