10.2. Study Endpoints and Analyses

10.2.1. Primary Endpoint and Analysis

10.2.1.1. Primary Endpoint

The clinical benefit rate (CBR) is defined as the number and proportion of participants who are assessed with either a complete response (CR), a partial response (PR), or stable disease (SD) prior to 1 year after treatment start and show no evidence of loss of response nor progression

within that year. Response and progression will be assessed according to the Revised Response Evaluation Criteria in Solid Tumors (RECIST) v1.1.

10.2.1.2. **Primary Analysis Plan**

The primary analysis will be the calculation of the clinical benefit rate, (CBR), defined as the percentage of subjects in the analysis population who achieve a complete response (CR), partial response (PR), or stable disease (SD) as measured at 12 months \pm 1 month (approximately 1 year) from the start of treatment. CR, PR, and SD are as defined by RECIST v1.1. (See Appendix C RECIST v1.1). The CBR and the two-sided 95% Clopper-Pearson (exact) confidence interval will be calculated.

The analysis population will include all subjects who started nirogacestat and underwent cryoablation. Subjects who withdraw from the study prior to start of treatment or before receiving cryoablation and completing 1 year of treatment will be replaced.

10.2.1.3. **Relevant Subset for Primary Objective and Endpoint**

Evaluable subjects are those subjects who have received cryoablation therapy and completed 1 year of treatment.

10.2.1.4. **Primary Objective and Endpoint Assessment Methods**

CBR will be evaluated on the basis of clinical response as measured using imaging by MRI scan and evaluated by RECIST v1.1 (Appendix C). Determination of response will be made by the treating investigator.

10.2.1.5. **Measurement Time Points for Primary Objective / Outcome**

Imaging will be performed at screening, then every 3 cycles (ie, every 12 weeks \pm 14 days) until End of Treatment. MRI scan will be used at screening and at subsequent time points.

10.2.2. **Secondary Endpoints and Analysis**

10.2.2.1. **Clinical Benefit Rate (CBR) assessed by modified RECIST**

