2.4.3. Best overall response: all time points

The best overall response is determined once all the data for the subject is known.

Best response determination in this trial where confirmation of complete or partial response IS NOT required: Best response in these trials is defined as the best response across all time points (for example, a subject who has SD at first assessment, PR at second assessment, and PD on last assessment has a best overall response of PR). When SD is believed to be best response, it must also meet the protocol specified minimum time from baseline. If the minimum time is not met when SD is otherwise the best time point response, the subject's best response depends on the subsequent assessments. For example, a subject who has SD at first assessment, PD at second and does not meet minimum duration for SD, will have a best response of PD. The same subject lost to follow-up after the first SD assessment would be considered non-evaluable.

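### The primary endpoint is defined in conflicting ways, and two of the definitions require neither a 12-month assessment nor survival to 1 year

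*Protocol*

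**What the plan says.** The protocol describes the primary endpoint, or who is counted in it, in several places.

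- **Section 2.3.2.1 (registered primary outcome):** complete response, partial response or "stable disease (SD) within 1 year and with no evidence of loss of response nor progression within that year".
- **Section 10.2.1.1 (primary endpoint):** the same categories, reached "prior to 1 year after treatment start and show no evidence of loss of response nor progression" within that year. This is close to 2.3.2.1 but not identical.
- **Section 10.2.1.2 (primary analysis):** complete response, partial response or "stable disease (SD) as measured at 12 months", with a window of 1 month either side.
- **Section 10.2.1.2 (population):** "The analysis population will include all subjects who started nirogacestat and underwent cryoablation".
- **Section 10.2.1.2 (replacement):** "Subjects who withdraw from the study prior to start of treatment or before receiving cryoablation and completing 1 year of treatment will be replaced".
- **Section 10.2.1.3:** the evaluable set is limited to subjects who had cryoablation and completed 1 year of treatment.
- **Section 2.3.2.2, Outcome 2 (mRECIST version):** opens with the same description as the primary outcome, then closes with "The outcome is the number of participants alive after 1 year and without PD per mRECIST". The primary outcome has no such closing line.
- **Appendix C, 2.4.3 (best overall response):** in an example where a required minimum duration of stable disease is not met, "The same subject lost to follow-up after the first SD assessment would be considered non-evaluable". The protocol gives no value for that minimum.

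**The concern.** Sections 2.3.2.1 and 10.2.1.1 set two conditions: one qualifying assessment before 1 year, and no evidence of loss of response or progression during the year. A subject who is no longer scanned can produce no such evidence, and nor can one who has died without a measured increase. The first on-study MRI is due before Cycle 4, and section 5.3 places the staging scan before cryoablation. The qualifying stable scan can therefore predate the procedure under study.

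Subjects with no later scan are foreseeable. Under 6.1 and 6.2.2, end-of-treatment imaging for those who stop for reasons other than progression is at the provider's discretion. Under 3.7.3, subjects who stop by their own choice but allow follow-up are followed by standard of care.

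In a single-arm study of about 20 subjects, a few such cases scored one way or the other can decide the conclusion. If the choice among the definitions is made after the data are seen, it is data-driven.

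**Working it through.** **1. The plan's own figure.** Section 10.4.2 gives 100.0% power for n = 20, null rate 0.5, alternative 0.8, one-sided exact test at 0.05. With X ~ Bin(20, p):

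- P(X ≥ 14 | 0.5) = 0.0577 and P(X ≥ 15 | 0.5) = 0.0207, so 15 is the smallest cut-off that holds 5%. Its power is P(X ≥ 15 | 0.8) = 80.4%.
- A power near 100% appears only at the cut-off of 11 in 10.4.4 (99.7%), where P(X ≥ 11 | 0.5) = 0.412.

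The stated power is not reproduced at the stated alpha. That is a separate matter. The cut-off of 15 is used below so that it does not mix with the effect of scoring.

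**2. Two example subjects under each rule.** Subject A has stable disease on the scan before Cycle 4, has cryoablation, stops at week 20 and is not scanned again. Subject B has stable disease and cryoablation and dies at month 8 with no measured progression.

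| Rule | A | B |
|---|---|---|
| 2.3.2.1 and 10.2.1.1, read literally | Benefit | Benefit |
| 10.2.1.2, status at 12 months | No status; not a success | No status; not a success |
| 10.2.1.2, analysis population | Included | Included |
| 10.2.1.2, replacement | Replaced if stopping counts as withdrawing from the study | Death not mentioned |
| 10.2.1.3, evaluable set | Outside | Outside |
| 2.3.2.2, Outcome 2 closing line | Progression status unknown | Not counted |
| Appendix C, 2.4.3 | Non-evaluable only if an unstated minimum is not met | Not addressed |
| 10.2.2.2, progression-free survival | Censored | Event |

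The same subject can be a success, a subject without a status, or outside the set. Subject B is a success on the primary wording and an event for progression-free survival.

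**3. Size, as an illustration.** Let m of 20 be such subjects (assumed) and let the other 20 − m have a true rate of 0.5.

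- Scored as success: P = P(Bin(20 − m, 0.5) ≥ 15 − m)
- Scored as failure: P = P(Bin(20 − m, 0.5) ≥ 15)
- Expected rate: (m + 0.5(20 − m))/20 against 0.5(20 − m)/20

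| m | P(≥ 15), success | P(≥ 15), failure | Expected rate, success / failure |
|---|---|---|---|
| 0 | 0.0207 | 0.0207 | 50% / 50% |
| 2 | 0.0481 | 0.0038 | 55% / 45% |
| 3 | 0.0717 | 0.0012 | 57.5% / 42.5% |
| 4 | 0.1051 | 0.0003 | 60% / 40% |

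For m = 4: (4 + 8)/20 = 60% and 8/20 = 40%.

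**The case against.** The strongest reply is that 2.3.2.1 is not the operative rule. The analysis section, 10.2.1.2, requires a status at 12 months, and the synopsis and objectives speak of the rate at 1 year. Section 10.2.1.3 admits only completers, and early withdrawals are replaced. On that view neither example subject is ever scored as a success. Outcome 2 also suggests that the authors took the shared sentence to imply survival.

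Much of this stands. A reader might infer that the trial will count missing scans and deaths as benefit. The documents do not support that, because 10.2.1.2 would not, and 10.2.1.3 would leave these subjects out.

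The reply does not remove the conflict:

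- Replacement applies to subjects who withdraw from the study. Section 3.7.2 keeps subjects whose therapy is stopped in follow-up if they allow it, so stopping drug is not clearly withdrawal. Death is not covered.
- The analysis population keeps everyone who started nirogacestat and had cryoablation, which contradicts a completers-only set.
- Section 3.5.1 says the date of first treatment may decide who enters the registry results, and those results use the wording of 2.3.2.1.

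Three further limits apply. Appendix C does not simply make the early leaver non-evaluable, because its example depends on a minimum duration that is never given. The phase 3 figure, "14 (20%) patients discontinued due to TEAEs", is discontinuation for adverse events, not loss of imaging within a year, so it does not show that 4 of 20 would be lost here. How to score a missing assessment could be left to an analysis plan, but here the protocol itself states rules that conflict.

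**Conclusion.** The point holds as a conflict of definitions and populations for the primary endpoint. Sections 2.3.2.1 and 10.2.1.1 require neither a 12-month assessment nor survival. Section 10.2.1.2 and Outcome 2 say otherwise, and the rules on who is counted disagree with each other.

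If the literal wording were applied with m = 2 to 4, the chance of reaching 15 of 20 at a true rate of 0.5 would be 4.8% to 10.5%, against 2.1% with none. At m = 4 the choice of scoring moves the expected rate by 20 points.

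These figures rest on an assumed m, on a rate of 0.5 in the other subjects, and on a cut-off of 15 that is not in the protocol. They show how sensitive the result is to scoring; they are not a forecast of bias.

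**What to change.** - Use one definition in 2.3.2.1, 10.2.1.1 and 10.2.1.2: alive at 1 year, no earlier progression by RECIST v1.1, and complete response, partial response or stable disease on the 12-month scan within its window.
- Score every subject in the analysis population (started nirogacestat and had cryoablation) who died or has no 12-month assessment as non-benefit.
- Align 10.2.1.3 and the replacement rule so that these subjects are neither dropped nor replaced in the primary analysis. State the success cut-off for the resulting denominator, which could reach 23. For 23 the exact 5% cut-off is 16 (type I error 0.0466).
- Report completers only, and last scan carried forward, as sensitivity analyses.
- Name the scheduled scan that serves as the 12-month scan. The scan before Cycle 13 falls at 12 × 28 = 336 days, or 322 to 350 days with the ± 14-day allowance. Eleven months is about 335 days (11 × 365/12), so an on-schedule scan can fall before the present window opens and would be scored as missing.

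The cost is protocol wording and two sensitivity rows. The reported rate may be lower: each subject rescored costs 1/20 = 5 points. With few such subjects the loss is small. At m = 4 with the others at 0.8, the expected rate is 64% instead of 84%, and the chance of at least 15 of 20 is 14.1% instead of 91.8%. Obtaining the 12-month scan in subjects who have stopped treatment therefore protects power as well as validity.

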2.3.2.2. Secondary Outcomes

- **Outcome 2 (Secondary) Title:** Clinical Benefit per mRECIST

Description: Clinical benefit (CB) is defined as the number of participants assessed with a complete response (CR), partial response (PR), or stable disease (SD) within 1 year and with no evidence of loss of response nor progression within that year.

Response & progression will be assessed according to the modified Revised Response Evaluation Criteria in Solid Tumors (mRECIST), as follows.

mRECIST:

- CR=Disappearance of intratumoral enhancement
- PR= $\geq 30\%$ decrease in the diameter of target lesion(s)
- PD=An increase of $>20\%$ in the diameter of target lesion.

The outcome is the number of participants alive after 1 year and without PD per mRECIST, a number without dispersion.

Time Frame: 1 year

- **Outcome 3 (Secondary) Title:** Progression-free Survival (PFS)

Description: Progressive-free survival (PFS) is an assessment of the number of participants at a specific time who remain alive and without tumor progression.

Progressive disease (PD) will be assessed according to Revised Response Evaluation Criteria in Solid Tumors (RECIST)v1.1, or, for tumors assessed with MRI enhancement, modified RECIST (mRECIST) defined as follows:

RECIST v1.1:

- PD=20% increase in diameter of target lesion; progression of non-target lesion; or ≥ 1 new lesion(s)

mRECIST:

- PD=An increase of $>20\%$ in the diameter of target lesion.

The outcome is the number of participants alive after 1 year and without PD per RECIST or mRECIST, a number without dispersion.

Time Frame: 1 year

- **Outcome 4 (Secondary) Title:** Objective Response

Description: Objective response (OR) is defined as the number of participants assessed with a complete response (CR) or partial response (PR) within 1 year and with no evidence of loss of response nor progression within that year. Response & progression will be assessed according to the Revised Response Evaluation Criteria in Solid Tumors (RECIST)v1.1, or, for assessed with MRI enhancement, modified RECIST (mRECIST) as follows:

RECIST v1.1:

- CR=Disappearance of all lesions
- PR= $\geq 30\%$ decrease in diameter of target lesions
- Progressive disease (PD)=20% increase in diameter of target lesion; progression of non-target lesion; or ≥ 1 new lesion(s)

mRECIST:

- CR=Disappearance of intratumoral enhancement
- PR= $\geq 30\%$ decrease in the diameter of target lesion(s)
- PD=An increase of $>20\%$ in the diameter of target lesion.

For the overall outcome:

- SD=Changes not meeting above criteria
- Overall Response (OR)=CR+PR
- CB=CR+PR+D

The outcome is the number of participants with OR per RECIST or mRECIST within 1 year, a number without dispersion.

Time frame: 1 year

- **Outcome 5 (Secondary) Title: Time-to-Response (TTR)**

Description: Time-to-response (TTR) is an assessment of the length of time from the start of treatment until clinical response (complete response, CR; or partial response, PR) is documented.in accordance with the Revised Response Evaluation Criteria in Solid Tumors (RECIST)v1.1, or, for assessed with MRI enhancement, modified RECIST (mRECIST) defined as follows:‘

RECIST v1.1:

- CR=Disappearance of all lesions
- PR= $\geq 30\%$ decrease in diameter of target lesions
- Progressive disease (PD)=20% increase in diameter of target lesion; progression of non-target lesion; or ≥ 1 new lesion(s)

mRECIST:

- CR=Disappearance of intratumoral enhancement
- PR= $\geq 30\%$ decrease in the diameter of target lesion(s)
- PD=An increase of $>20\%$ in the diameter of target lesion.

For either:

- SD=Changes not meeting above criteria

The outcome is expressed as the median TTR (by RECIST or mRECIST), with standard deviation.

Time Frame: 1 year

- **Outcome 6 (Secondary) Title: Duration of Response (DoR)**

Description: Duration of response (DoR) is defined as the time from the date of documented disease response (complete response, CR; or partial response, PR) to the date of the first documented disease progression. CR and PR will be assessed according to the Revised Response Evaluation Criteria in Solid Tumors (RECIST)v1.1, or, for assessed with MRI enhancement, modified RECIST (mRECIST) as follows:

RECIST v1.1:

- CR=Disappearance of all lesions
- PR= $\geq 30\%$ decrease in diameter of target lesions
- Progressive disease (PD)=20% increase in diameter of target lesion; progression of non-target lesion; or ≥ 1 new lesion(s)

mRECIST:

- CR=Disappearance of intratumoral enhancement
- PR= $\geq 30\%$ decrease in the diameter of target lesion(s)
- PD=An increase of $>20\%$ in the diameter of target lesion.

For both:

- SD=Changes not meeting above criteria

The outcome is expressed as the median DoR, with standard deviation. Participants alive with a clinical response and without progression 24 months after treatment will be censored at that time.

Time Frame: 2 year

- **Outcome 7 (Secondary) Title: Related Adverse Events (AEs)**

Description: Safety is assessed as the number of adverse events determined by the investigator to be possibly, probably, or definitely related to nirogacestat treatment (ie, drug toxicities). All related events will be collected and reported. Adverse events of Grade 3 (severe) are considered notable and potentially actionable during treatment, while adverse events Grade 1 or 2 are considered routine, with typically little or no change in treatment needed. The outcome will be reported as the number of related adverse events Grade 3 or higher is a number without dispersion.

Time Frame: 1 year

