For tumors with MRI enhancement, CBR will be evaluated on the basis of clinical response as measured using imaging by MRI scan and evaluated by modified RECIST (Appendix D). Determination of response will be made by the treating investigator. Imaging will be performed at screening, then every 3 cycles (ie, every 12 weeks \pm 14 days) until End of Treatment. MRI scan will be used at screening and at subsequent time points.

10.2.2.2. **Median Progression-free Survival (PFS)**

Median progression free survival (PFS) will be measured using imaging by MRI scan and evaluated by RECIST v1.1, mRECIST, and volumetrically (change in tumor volume as assessed by MRI volumetric).

Progression-free survival is defined as the time from start of treatment to date of progression or death due to any cause. If a subject is not known to have progressed or died, then PFS will be censored at the latest date the subject was known to be alive or progression-free (on or before the cut-off date). The PFS distribution will be estimated using the Kaplan-Meier method, and

the Kaplan-Meier curves, medians and 95% confidence intervals of the medians will be presented.

10.2.2.3. **Objective Response Rate (ORR) at 1 year**

For the objective response rate (ORR) at 1 year, the percentage of subjects who start study treatment and achieve an objective response (CR or PR) will be calculated. ORR will be measured using imaging by MRI scan and evaluated both RECIST v1.1, mRECIST, and MRI volumetric.

The ORR will be calculated as the proportion of subjects with objective response. The ORR and the two-sided 95% Clopper-Pearson (exact) confidence interval will be calculated.

10.2.2.4. **Time to Response (TTR)**

Time to response is defined as the time from the start of treatment with nirogacestat to the first objective tumor response (CR or PR), and will be measured using imaging by MRI scan and evaluated by RECIST v1.1, mRECIST, and volumetrically.

The TTR distribution will be estimated using the Kaplan-Meier method, and the Kaplan-Meier curves, medians and 95% confidence intervals of the medians will be presented.

10.2.2.5. **Duration of Response (DoR)**

Duration of response (DoR) is defined as the time from the date of documented disease response (CR or PR) to the date of the first documented progression, and will be determined using imaging by MRI scan and evaluated by RECIST v1.1, mRECIST, and volumetrically.

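### Registered PFS and objective response are single pooled RECIST-or-mRECIST counts, in conflict with the Kaplan-Meier PFS and per-criterion response rate defined in Section 10.2.2

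*Protocol*

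**What the plan says.** **Registered definitions (Protocol Section 2.3.2.2).** Outcome 3 describes PFS as something that "is an assessment of the number of participants at a specific time who remain alive and without tumor progression". Progression is judged by RECIST v1.1, "or, for tumors assessed with MRI enhancement, modified RECIST (mRECIST) defined as follows". The result to be posted is: "The outcome is the number of participants alive after 1 year and without PD per RECIST or mRECIST, a number without dispersion". Outcome 4 takes the same form: "The outcome is the number of participants with OR per RECIST or mRECIST within 1 year, a number without dispersion". Its description also requires the response to be seen "within 1 year and with no evidence of loss of response nor progression within that year". Neither outcome states a denominator, a confidence interval, or what to do with a subject who has no one-year assessment.

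**Analysis definitions (Protocol Section 10.2.2).** Section 10.2.2.2 states: "Progression-free survival is defined as the time from start of treatment to date of progression or death due to any cause". It adds a censoring rule, "If a subject is not known to have progressed or died, then PFS will be censored at the latest date", and an estimator: "The PFS distribution will be estimated using the Kaplan-Meier method", with medians and their 95% confidence intervals. Section 10.2.2.3 defines ORR at one year as a percentage of subjects who start study treatment, with a two-sided 95% Clopper-Pearson interval. Both endpoints are evaluated by RECIST v1.1, mRECIST and MRI volumetry. The synopsis names the same three criteria and also specifies median PFS.

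**The concern.** One endpoint name carries two definitions, and no text connects them. A one-year count cannot yield the median that the synopsis and Section 10.2.2.2 promise. A single number resting on two criteria cannot be compared with either criterion-specific result.

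The criteria differ in substance. As written in Section 2.3.2.2, RECIST v1.1 progression includes new lesions and non-target progression, while mRECIST progression lists only growth of the target lesion. A subject with a new lesion has therefore progressed under one and not under the other. Appendix D explains that mRECIST was proposed for treatment that causes necrosis without overall shrinkage, and every subject here is planned for subtotal cryoablation, so response may also differ by criterion.

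At stake is the public record of two secondary endpoints. Section 2.3.1 says the protocol with its statistical analysis will be posted in the ClinicalTrials.gov results record, so the posted count would stand beside an analysis section that defines something else.

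**Working it through.** The plan states no figure for PFS or ORR that could be reproduced, so the check is a comparison of text followed by illustrations.

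**1. Side by side**

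| Item | Section 2.3.2.2 | Sections 10.2.2.2 and 10.2.2.3 |
|---|---|---|
| PFS quantity | Number progression-free at 1 year | Time to progression or death |
| PFS summary | Count, no dispersion | Kaplan-Meier curve, median, 95% CI |
| Subjects without 1-year status | No rule | Censored when last known alive or progression-free |
| Response summary | Count, no dispersion | Percentage of treatment starters, exact 95% CI |
| Response durability | No loss or progression in the year | Not required |
| Criteria | RECIST v1.1 or mRECIST, in one number | RECIST v1.1, mRECIST, MRI volumetry |

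**2. Count against Kaplan-Meier.** From the protocol: up to 23 subjects enrolled. Assumed, not in the protocol: all 23 start treatment; 4 progress, at weeks 12, 24, 36 and 48; c subjects are censored progression-free at week 13; the rest are followed beyond week 52. The count scored over all starters is (23 − 4 − c)/23. The Kaplan-Meier estimate at week 52 is the product of (1 − events/at risk) over the four progression times. The week-12 factor is 22/23. The three later factors telescope to (19 − c)/(22 − c).

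- c = 0: count 19/23 = 82.6%; Kaplan-Meier 22/23 × 19/22 = 82.6%.
- c = 1: count 18/23 = 78.3%; Kaplan-Meier 22/23 × 18/21 = 82.0%.
- c = 3: count 16/23 = 69.6%; Kaplan-Meier 22/23 × 16/19 = 80.5%.
- c = 5: count 14/23 = 60.9%; Kaplan-Meier 22/23 × 14/17 = 78.8%.

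If the three subjects in the c = 3 case were dropped instead of scored as failures, the count would give 16/20 = 80.0%. Section 2.3.2.2 does not choose between 69.6% and 80.0%.

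**3. The pooled criterion for PFS.** Assume 20 subjects with 4 progressions under each criterion, so each criterion alone leaves 16 progression-free.

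- If progression under either criterion disqualifies, the count runs from 20 − (4 + 4) = 12 (no overlap) to 20 − 4 = 16 (full overlap).
- If being progression-free under one criterion suffices, it runs from 16 (full overlap) to 20 (no overlap).
- If each tumor is assigned one criterion, each subject's status lies between these two rules, so the count lies between 12 and 20.

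**4. The pooled criterion for response.** Assume 20 subjects with 4 responders by RECIST v1.1 and 10 by mRECIST. Reported separately, these are 4/20 = 20% (exact 95% CI 5.7 to 43.7) and 10/20 = 50% (27.2 to 72.8). A count in which either criterion suffices is between 10 and 14. It hides the 30-point difference between the criteria.

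**The case against.** The strongest reply is that Section 2.3.2 governs registry reporting and Section 10 governs analysis. A one-year PFS status and a Kaplan-Meier median can both be reported, and the primary outcome is also registered without dispersion although Section 10.2.1.2 plans an exact interval for it. That shows the format is habitual. It does not explain the conflict: in the same section, Outcomes 5 and 6 are registered as medians, and Outcome 6 has a censoring rule. The format plainly allows time-to-event summaries.

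Four stronger readings are tempting and are not supported.

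- **Best of two criteria.** A reader might infer that each subject is scored by whichever criterion is favourable, so that pooling can only raise the response count. The clause on tumors assessed with MRI enhancement points more naturally to one criterion per tumor. On that reading the count can fall below the higher single-criterion count, and for PFS it can fall below both. Mixing criteria is a fault on either reading.
- **Censoring in both outcomes.** Objective response is binary. Its gap is the missing denominator and the lack of a rule for unevaluable subjects.
- **A large gap implied by drug discontinuation.** In the phase 3 trial summarised in Section 1.2.4, 23% stopped nirogacestat for adverse events (20% once clinical progression is excluded). A reader might take this as the share lost before one year. No timing is given, and stopping drug is not censoring. Section 3.7.2 keeps subjects who allow it in follow-up on the study schedule, and Section 3.7.3 keeps those who stop by choice in standard-of-care follow-up. Missing status remains possible, because imaging at the End of Treatment visit is discretionary for subjects who stop for reasons other than progression.
- **Full duplication of Outcome 2.** The result sentence of Outcome 2 matches the mRECIST part of Outcome 3. However, its description adds a no-loss-of-response condition, and Outcome 3 also covers RECIST v1.1. The overlap is partial.

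**Conclusion.** The conflict is on the face of the protocol. Outcomes 3 and 4 differ from Sections 10.2.2.2 and 10.2.2.3 in quantity, summary and set of criteria. The response outcome also differs in its durability condition.

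The size in this trial cannot be known from the documents. The PFS count agrees with Kaplan-Meier when every subject has one-year status. It falls below when subjects without that status are scored as not progression-free, by about 11 points in the assumed case of 3 censored early among 23. The pooled criterion is indeterminate: 4 progressions in 20 under each criterion allow any count from 12 to 20. These figures rest on assumed event times, losses and overlaps.

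The consequence is confined to secondary outcomes. The primary clinical benefit test and the sample size do not depend on it. It should be corrected, because followed as written the registered results would not be the results Section 10 plans.

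**What to change.** In Section 2.3.2.2 and the registry entry:

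- Restate Outcome 3 as Kaplan-Meier PFS with the Section 10.2.2.2 censoring rule, giving the median and the one-year estimate, each with a 95% CI.
- Restate Outcome 4 as n/N among subjects who start study treatment, with a 95% Clopper-Pearson interval.
- Report each outcome separately for RECIST v1.1, mRECIST and MRI volumetry, and delete the pooled count. Listing only the first two would leave part of the mismatch in place.
- Make the loss-of-response condition the same in Sections 2.3.2.2 and 10.2.2.3, either required in both or in neither.

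The cost is a wording amendment and a registry update. The Kaplan-Meier and exact-interval analyses by all three criteria are already planned; the one-year estimate is read from the same curve. No further data or subjects are needed.
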